3.2. Final Analyses

The final planned primary analyses will be performed after the completion of the following sequential steps:

1. All participants have completed the study as defined in the protocol
2. All required database cleaning activities have been completed and final database release (DBR) and database freeze (DBF) has been declared by Data Management.
3. All criteria for unblinding the randomization codes have been met.
4. Randomization codes have been distributed according to RandAll NG procedures.

4. ANALYSIS POPULATIONS

Population	Definition / Criteria	Analyses Evaluated
Screened	
 • All participants who were screened for eligibility 	
 • Study Population
Enrolled	
 • All participants who passed screening and entered the study. • Note screening failures (who never passed screening even if rescreened) and participants screened but never enrolled into the study (Reserve, Not Used) are excluded from the Enrolled population as they did not enter the study. 	
 • Study Population
Safety	
 • All randomized participants who received at least one dose of study treatment. • Participants will be analyzed according to the intervention they received. 	
 • Study Population • Safety
Pharmacokinetic (PK)	
 • The PK Population will include all participants who undergo plasma or urine PK sampling and have evaluable PK assay results. 	
 • PK analyses

Refer to [Appendix 10](#) which details the population used for each display.

4.1. Protocol Deviations

Important protocol deviations (including deviations related to study inclusion/exclusion criteria, conduct of the trial, patient management or patient assessment) will be summarised and listed.

Separately, any important deviations which result in exclusion from analysis populations and events that result in exclusion from analysis populations will be listed.

Protocol deviations will be tracked by the study team throughout the conduct of the study in accordance with the Protocol Deviation Management Plan v1.0 June 2020

- Data will be reviewed prior to unblinding and freezing the database to ensure all important deviations and deviations which may lead to exclusion from the analysis populations are captured and categorised on the protocol deviations dataset.
- This dataset will be the basis for the summaries and listings of protocol deviations.

A separate listing of all inclusion/exclusion criteria deviations will also be provided. This summary will be based on data as recorded on the inclusion/exclusion page of the eCRF.

5. CONSIDERATIONS FOR DATA ANALYSES AND DATA HANDLING CONVENTIONS

5.1. Study Treatment & Sub-group Display Descriptors

Treatment comparisons of relative bioavailability and food effect will be displayed as follows using the descriptors respectively:

1. (B vs. A): VH3739937 X 100 mg (single dose given as 100 mg tablet(s)) administered under moderate fat conditions (test) vs. VH3739937 X 100 mg (single dose oral suspension of VH3739937 dispersion) administered under moderate fat conditions (reference)
2. (B vs. C): VH3739937 X 100 mg (single dose given as 100 mg tablet(s)) administered under moderate fat conditions (test) vs. VH3739937 X 100 mg (single dose given as 100 mg tablet(s)) administered under fasted conditions (reference).

Treatment Group Descriptions			
RandAll NG		Data Displays for Reporting	
Code	Description	Description	Order in TLF
Part 1			
P	Placebo	SD PBO	1
D1	GSK3739937 Dose Level 1	SD 10mg	2
D2	GSK3739937 Dose Level 2	SD 30mg	3
D3	GSK3739937 Dose Level 3	SD 80mg	4
D4	GSK3739937 Dose Level 4	SD 160mg	5
D5	GSK3739937 Dose Level 5	SD 320mg	6
D6	GSK3739937 Dose Level 6	SD 640mg	7
D7	GSK3739937 Dose Level 7 800 mg	SD 800mg	8
Part 2			
RP	Placebo Repeated Dose	QD PBO	9
R1	GSK3739937 Repeat Dose Level 1	QD 25mg	10
R2	GSK3739937 Repeat Dose Level 2	QD 50mg	11
R3	GSK3739937 Repeat Dose Level 3	QD 100 mg	12
WP	Weekly Placebo	QW PBO	13
W1	GSK3739937 Weekly Repeat Dose 500 mg	QW 500mg	14
Part 3			
A	GSK3739937 PiB Fed 100 mg	PiB Fed	15
B	GSK3739937 Tablet Fed 100 mg	Tablet Fed	16
C	GSK3739937 Tablet Fasted 100 mg	Tablet Fasted	17

NOTES:

- Order represents treatments being presented in TFL, as appropriate.

5.2. Baseline Definitions

For all endpoints (except as noted in baseline definitions) the baseline value will be the latest pre-dose assessment with a non-missing value, including those from unscheduled visits. If time is not collected, Day 1 assessments are assumed to be taken prior to first dose and used as baseline.

Part 1 (SAD Cohorts 1 and 2)

Parameter	Study Assessments Considered as Baseline			Baseline Used in Data Display
	Screening	Day -1	Day 1 (Pre-Dose)	
Lab	X	X		Day -1
ECG	X	X	X	Day 1 (Pre-Dose)
Vital Signs	X	X	X	Day 1 (Pre-Dose)

Part 2 (MAD Cohorts 3, 4, 5, and 6)

Parameter	Study Assessments Considered as Baseline			Baseline Used in Data Display
	Screening	Day -1	Day 1 (Pre-Dose)	
Lab	X	X	X	Day 1 (Pre-Dose)
ECG	X	X	X	Day 1(Pre-Dose)
Vital Signs	X	X	X	Day 1 (Pre-Dose)

Part 3 (RBA/FE)

Parameter	Study Assessments Considered as Baseline			Baseline Used in Data Display
	Screening	Day -1	Day 1 (Pre-Dose)	
Lab	X	X		Day -1
ECG	X	X	X	Day 1 (Pre-Dose)
Vital Signs	X	X	X	Day 1 (Pre-Dose)

On Day 1 triplicate pre-dose ECGs will be performed. The baseline for every ECG parameter will be calculated as the average of that parameter's values from the Day 1 pre-dose triplicate ECG reading

On Day 1 three readings of blood pressure and pulse will be taken. The first reading will be rejected. The average of the second and third readings (as recorded in the CRF) will serve as baseline.

Unless otherwise stated, if baseline data is missing no derivation will be performed and baseline will be set to missing.

For Part 3, baseline will be rederived for each period.

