SARS-CoV-2 Test	X					X								X					An approved molecular test (PCR) will be used. If participants remain in unit during study treatment periods, weekly SARS-CoV-2 testing is required. If participants are discharged from unit on Day 6, SARS-CoV2 test will be required at discharge, approximately one week prior to re-admission to the unit for the following period and at Day -2. For further detail, see Appendix 7 and Section 8.1.3	
Drug/alcohol/nicotine screen	X																			
Vital Signs		X	X	X	X	X	X	X	X		X	X	X	X	X	X	X	Blood pressure and pulse will be measured in triplicate pre-dose on Day 1 in Periods 1-3. At all other timepoints, single blood pressure and pulse will be measured at pre-dose timepoint. Temperature will be monitored every day during study participation. For further detail, see Section 8.1.2		
CSSRS		X				X							X							

Procedure	Pre-Treatment Days		Treatment Periods 1 and 2 (Days)								Treatment Period 3 only (Days)								Notes			
	-2	-1	1	Washout								1	Washout									
				2	3-5	6	9	12	16	17-22	2		3-5	6	9	12	16					
VH3739937 Dose Administration			X									X								Randomization to occur on Day 1 prior to dosing. For meal instructions prior to dose, see Section 5.3.1		
12-Lead Safety ECGs		X	X			X	X	X	X			X			X	X	X	X	All ECG timepoints on Day 1 in Periods 1-3 will be taken at pre-dose, 2 h and 4 h post dose. Pre-dose ECGs in Periods 1-3 will be taken in triplicate. For further detail, see Section 8.1.4			
Plasma PK Sampling			X	X	X	X	X	X	X			X	X	X	X	X	X	X	2mL of blood will be collected at pre-dose (within 15 mins prior to dosing) and 1, 2, 3, 4, 5, 6, 7, 8, 9, 10, 12, 16, 24, 48, 72, 96, 120, 192, 264, 360 h post dose. For further detail, see Section 8.4. Please see SRM for details of blood collection and processing.			
Haematology/ Chemistry/Urine Test		X		X		X	X	X	X			X		X	X	X	X	X	Day -1 assessments will be collected prior to dosing periods for all treatment periods. Day 2 samples in each period to be collected 24 h post dose. For further detail, see Appendix 2			
SAE review	←-----→																		All SAEs will be collected from screening until follow up visit			

Procedure	Pre-Treatment Days		Treatment Periods 1 and 2 (Days)								Treatment Period 3 only (Days)						Notes		
	-2	-1	1	Washout								1	Washout						
				2	3-5	6	9	12	16	17-22	2	3-5	6	9	12	16			
AE review				←-----→								→						All AEs will be collected from first dose until follow up visit	
Concomitant medications	←-----→																		

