8.1.2. Vital Signs

- Single oral temperature, pulse rate, respiratory rate and blood pressure will be assessed.
- All blood pressure and pulse measurements will be assessed in semi-supine position with a completely automated device. Manual techniques will be used only if an automated device is not available.
- Blood pressure and pulse measurements will be preceded by at least 5 minutes of rest for the participant in a quiet setting without distractions (e.g., television, cell phones).
- Vital signs (to be taken before blood collection for laboratory tests) will consist of 1 pulse and 3 blood pressure measurements (3 consecutive blood pressure readings will be recorded at intervals of at least 1 minute). In addition, temperature will be monitored daily during study participation.
- Additional details can be found in the SRM.

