7.3. Other Safety Analyses

The analyses of non-laboratory safety test results including ECGs and vital signs will be based on GSK Core Data Standards, unless otherwise specified. The details of the planned displays are presented in [Appendix 10](#)

For worst-case results post baseline relative to baseline for vital signs, the average of any triplicate measurement, if taken, will be considered.

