13.6. Appendix 6: Derived and Transformed Data

13.6.1. General

Multiple Measurements at One Analysis Time Point

 Mean of the measurements will be calculated and used in any derivation of summary statistics but if listed, all data will be presented. Participants having both High and Low values for Normal Ranges at any post-baseline visit for safety parameters will be counted in both the High and Low categories of “Any visit post-baseline” row of related summary tables. This will also be applicable to relevant Potential Clinical Importance summary tables.
Study Day

 Calculated as the number of days from First Dose Date: 
 Ref Date = Missing → Study Day = Missing Ref Date < First Dose Date → Study Day = Ref Date – First Dose Date Ref Date ≥ First Dose Date → Study Day = Ref Date – (First Dose Date) + 1

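### Vital-sign baseline drops the first reading but post-baseline values do not, and the rule needs three pulse readings where Protocol 8.1.2 takes one

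*SAP*

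**What the plan says.** **Baseline.** SAP 5.2: "On Day 1 three readings of blood pressure and pulse will be taken". Then: "The first reading will be rejected". Then: "The average of the second and third readings (as recorded in the CRF) will serve as baseline". The same section averages the whole triplicate for the ECG baseline.

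**After baseline.** For worst-case vital signs, SAP 7.3 says that "the average of any triplicate measurement, if taken, will be considered". For several measurements at one time point, SAP 13.6.1 says: "Mean of the measurements will be calculated and used in any derivation of summary statistics but if listed, all data will be presented". Neither rule rejects a reading.

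**Number of readings.** Protocol 8.1.2 says that an assessment consists of "1 pulse and 3 blood pressure measurements", although its first bullet describes single measurements, blood pressure included. In Part 3, Protocol Table 6 has triplicate blood pressure and pulse before dosing on Day 1 of each period, and then: "At all other timepoints, single blood pressure and pulse will be measured at pre-dose timepoint".

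**Missing baseline.** SAP 5.2 has a general rule that takes the latest non-missing pre-dose value, except where a specific definition applies. It lists Screening and Day -1 as assessments considered for the vital-sign baseline. It also says that a missing baseline stays missing with no derivation unless stated otherwise.

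**Use.** Vital-sign change from pre-dose values is part of the primary safety endpoint (Protocol 3, SAP 2.2). SAP 13.8.4 sets change limits of 40 mmHg systolic, 20 mmHg diastolic and 30 bpm. These feed Table 3.35, a headline deliverable, and Listing 26.

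**The concern.** A change from baseline is interpretable when both values are built in the same way. Here the baseline leaves out the first reading, the later values in Parts 1-2 include it, and each later value in Part 3 is a lone reading. Any systematic difference between first and later readings therefore enters the change and has nothing to do with the drug. The rejection rule itself suggests that the SAP regards first readings as less representative.

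For pulse, the rule presupposes second and third readings that Protocol 8.1.2 does not provide. Outside the Part 3 Day 1 triplicate, there is nothing to average.

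At stake are the change-based flags in Table 3.35 and whether two programmers would produce the same heart-rate table from the same data.

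**Working it through.** The documents give no figure on this point, so there is none to reproduce. The check counts readings and derives the offset when there is no drug effect.

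**Readings left for baseline after the first is rejected**

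- Blood pressure: 3 - 1 = 2.
- Pulse, Parts 1-2 (one reading, Protocol 8.1.2): 1 - 1 = 0.
- Pulse, Part 3 Day 1 (three readings, Table 6): 3 - 1 = 2.

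**Offset in blood pressure change**

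Let d be the first reading minus the mean of readings 2 and 3, the same at every assessment. A single reading is assumed to behave like a first reading. Set the level of readings 2 and 3 to zero.

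- Baseline = mean of readings 2 and 3 = 0.
- Parts 1-2, post-baseline mean of three = (d + 0 + 0)/3, so the offset is d/3.
- Part 3, post-baseline single reading = d, so the offset is d.
- If single blood pressure readings were taken in Parts 1-2, as the first bullet of Protocol 8.1.2 allows, the offset there would also be d.

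| Assumed d (mmHg) | Parts 1-2, triplicate | Part 3, single |
|---|---|---|
| 0 | 0 | 0 |
| 2 | 0.67 | 2 |
| 5 | 1.67 | 5 |
| 10 | 3.33 | 10 |

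**Effect on the diastolic change flag (20 mmHg)**

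Take the change as normal with mean equal to the offset b. Its SD is not in the documents, and 8 and 10 mmHg are assumed. The increase flag rate is 1 - Φ((20 - b)/SD). The decrease flag rate is Φ((-20 - b)/SD). At d = 5:

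| SD | Flag | No offset | Parts 1-2 (b = 1.67) | Part 3 (b = 5) |
|---|---|---|---|---|
| 8 | Increase | 0.62% | 1.10% | 3.04% |
| 8 | Decrease | 0.62% | 0.34% | 0.09% |
| 10 | Increase | 2.28% | 3.34% | 6.68% |
| 10 | Decrease | 2.28% | 1.51% | 0.62% |

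A negative d would reverse the direction.

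**If all readings are averaged on both sides**

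- Parts 1-2 with triplicates: d/3 - d/3 = 0.
- Part 3: d - d/3 = 2d/3, so an offset remains.
- Part 3 with the first Day 1 reading as baseline: d - d = 0.

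**Price of the last option.** With equal independent reading error of variance 1, the error variance of the change is 1 + 1/2 = 1.5 with a two-reading baseline and 1 + 1 = 2 with a one-reading baseline. The ratio is 2/1.5 = 1.33, about one-third higher.

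**Pulse baseline in Parts 1-2.** Three outcomes are compatible with SAP 5.2: missing (the only value is rejected), the single value (the rule is not applied because its premise fails), or a Day -1 or Screening value (general rule). The text does not choose between them.

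**The case against.** The documents give no first-reading effect, and Protocol 8.1.2 requires at least five minutes of quiet rest before measurement, which should limit one. At d = 0 there is no offset. This stands: the size and sign are unknown.

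In Parts 1-2, active and placebo are measured alike. In Part 3, baseline is rederived each period and all treatments share one schedule. A common offset therefore cancels in mean contrasts in every part. This stands too. A reader might infer that the mismatch would look like a treatment effect in Part 3 because that part has no placebo. The documents do not support this for tablet versus powder-in-bottle or fed versus fasted. Only the uncontrolled change within a treatment is exposed.

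Appendix 10 of the SAP plans no table of mean vital-sign change, the change limits are wide, and the absolute limits need no baseline. None of the listed criteria in Protocol 7.1.4 and 7.1.5 uses a vital-sign change. This limits the consequences, but Table 3.35 still counts individual flags, and these move with the offset.

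A reader might also infer that the pulse baseline is missing for all 58 participants in Parts 1-2 (18 + 40). That goes too far. The reject-first rule is premised on three readings, the general rule offers a fallback, and the CRF and study reference manual, which might settle what is recorded, are not available here. The count is not firm either: SAP 2.3 describes nine new participants for 800 mg, which would make 67.

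**Conclusion.** The baseline and post-baseline constructions differ, and the pulse rule cannot be applied as written in Parts 1-2. Both follow from the text.

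The numerical consequence is conditional. The offset is d/3 in Parts 1-2 where triplicates are taken and d in Part 3, assuming that d is constant and that a lone reading behaves like a first one. To call the blood pressure changes biased without that condition would go beyond the documents. If d is not zero, the within-participant change flags in Table 3.35 shift, most in Part 3, while mean contrasts between arms or treatments are protected.

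The pulse baseline is undefined rather than known to be missing. The 30 bpm change criterion in Parts 1-2 depends on which of the three readings of SAP 5.2 is programmed. Since the correction is cheap, it should be made before Table 3.35 is produced.

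**What to change.** 1. In SAP 5.2, average all readings at a time point for the vital-sign baseline, as SAP 7.3 and 13.6.1 already do after baseline and as SAP 5.2 does for ECG. Rejecting the first reading at every triplicate time point would also align Parts 1-2, but it cannot be applied to the single readings in Part 3.
2. State that the single Day 1 pre-dose pulse is the baseline where only one is taken.
3. For Part 3, add a sensitivity version of the change flags with the first Day 1 reading as baseline, because averaging all three leaves 2d/3. The sensitivity version has a noisier baseline: the error variance of the change is about one-third higher than with a two-reading baseline. It should therefore be read beside the main version and not replace it.
4. Reconcile Protocol 8.1.2 (single versus three blood pressure readings, and one pulse) with SAP 5.2. SAP 2.1 reports no departure from the protocol's planned analysis, so the difference is not declared there.

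The cost is SAP wording, a clarification of Protocol 8.1.2 and one extra version of the Part 3 display. No new data are needed.

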5.3. Other Considerations for Data Analyses and Data Handling Conventions

Other considerations for data analyses and data handling conventions are outlined in the appendices:

Section	Component
13.3	Appendix 3 : Assessment Windows
13.4	Appendix 4 : Study Phases and Treatment Emergent Adverse Events
13.5	Appendix 5 : Data Display Standards & Handling Conventions
13.6	Appendix 6 : Derived and Transformed Data
13.7	Appendix 7 : Reporting Standards for Missing Data
13.8	Appendix 8 : Values of Potential Clinical Importance

6. STUDY POPULATION ANALYSES

6.1. Overview of Planned Study Population Analyses

The study population analyses will be based on the Safety population, unless otherwise specified.

Study population analyses including analyses of participant's disposition, protocol deviations, demographic and baseline characteristics, prior and concomitant medications, and exposure and treatment compliance will be based on GSK Core Data Standards. Details of the planned displays are presented in [Appendix 10](#).

7. SAFETY ANALYSES

The safety analyses will be based on the safety population, unless otherwise specified.

Safety data are the primary endpoints of the study, will be presented in tabular format and summarized descriptively accordingly to GSK's Integrated Data Standards Library (IDSL) standards.

7.1. Adverse Events Analyses

Adverse events analyses including the analysis of adverse events (AEs), Serious (SAEs) and other significant AEs will be based on GSK Core Data Standards. The details of the planned displays are provided in [Appendix 10](#) Adverse Events of Special Interest Analyses

A comprehensive list of MedDRA terms based on clinical review will be used to identify each type of event. Changes to the MedDRA dictionary may occur between the start of the study and the time of reporting and/or emerging data from on-going studies may highlight additional adverse events of special interest, therefore the list of terms to be used for each event of interest and the specific events of interest will be based on the safety review team (SRT) agreements in place at the time of reporting. While VH3739937 does not have a defined list of AESI, the AESI for the similar compound GSK3640254 will be used for this study. Further details of specific SOCs and SMQs for AESI of GS3640254 are maintained by that compound's SRT. The list broadly includes the following items:

- QT prolongation
- GI intolerance/toxicity
- Psychiatric events
 - Suicidal ideation/behaviour
 - Depression
 - Bipolar disorder Psychosis
 - Anxiety
 - Sleep disorders
 - Nervous system disorders

The details of the planned displays are provided in [Appendix 10](#)

7.2. Clinical Laboratory Analyses

The safety analyses will be based on the Safety population, presented by treatment group unless otherwise specified.

The ADLB dataset will be used, which contains the data that is available at a particular timepoint, with no imputation for missing values, unless otherwise stated in [Appendix 7](#).

Laboratory values, and change from baseline for haematology, clinical chemistry, and liver function parameters will be summarized by visit and by treatment group, based on GSK Core Data Standards. Laboratory values for haematology, clinical chemistry, liver function, and urinalysis will also be listed by subject. In addition, the worst-case results

post baseline relative to baseline relative to normal range will be reported for haematology, and clinical chemistry. The details of the planned displays are in [Appendix 10](#)

7.3. Other Safety Analyses

The analyses of non-laboratory safety test results including ECGs and vital signs will be based on GSK Core Data Standards, unless otherwise specified. The details of the planned displays are presented in [Appendix 10](#)

For worst-case results post baseline relative to baseline for vital signs, the average of any triplicate measurement, if taken, will be considered.

8. PHARMACOKINETIC ANALYSES

The pharmacokinetic (PK) analyses will be based on the Pharmacokinetic population, unless otherwise specified.

As an overview, individual, mean and median plasma VH3739937 concentration-time profiles will be plotted by treatment and day (for MAD) (linear and semi-log profiles). PK sampling times will be related to the start of the dosing date/time. Actual sampling times will be used to calculate all non-compartmental pharmacokinetic parameters. Individual concentrations of VH3739937 in plasma will be listed and summarised by treatment and nominal time.

8.1. Primary Pharmacokinetic Analyses

8.1.1. Endpoint / Variables

8.1.1.1. Drug Concentration Measures

Refer to [Appendix 5](#): Data Display Standards & Handling Conventions (Section 13.5.3 Reporting Standards for Pharmacokinetic)

8.1.1.2. Derived Pharmacokinetic Parameters

Pharmacokinetic parameters will be calculated by standard non-compartmental analysis according to current working practices and using the currently supported version of WinNonlin. All calculations of non-compartmental parameters will be based on actual sampling times. Pharmacokinetic parameters listed will be determined from the plasma concentration-time data, as data permits.

Parameter	Parameter Description
AUC(0-inf)	Area under the concentration-time curve extrapolated to infinity will be calculated as: AUC = AUC(0-t) + C(t) / lambda_z
AUC(0-t)	Area under the concentration-time curve from time zero to the time of the last quantifiable concentration (C(t)) will be calculated using the linear trapezoidal rule for each incremental trapezoid and the log trapezoidal rule for each decremental trapezoid.
AUC(0-24)	Area under the plasma concentration time curve from zero to 24 hrs
AUC(0-168)	Area under the plasma concentration time curve from zero to 168 hrs
AUC(0- τ)	Area under the curve (Area under the plasma drug concentration-time curve from pre-dose to the end of the dosing interval at steady state)
%AUCex	The percentage of AUC (0-inf) obtained by extrapolation (%AUCex) will be calculated as: [AUC(0-inf) – AUC(0-t)] / AUC(0-inf) x 100
C _{max}	Maximum observed concentration, determined directly from the concentration-time data.
C ₂₄	Concentration at 24 hours post-dose
C ₁₆₈	Concentration at 168 hours post-dose
C _{last}	Last quantifiable concentration

Parameter	Parameter Description
$C\tau$	Pre-dose (trough) concentration at the end of the dosing interval
t_{max}	Time to reach C_{max} , determined directly from the concentration-time data.
$t_{1/2}$	Apparent terminal half-life will be calculated as: $t_{1/2} = \ln 2 / \lambda_{z}$
t_{lag}	Absorption lag time
t_{last}	Time of last quantifiable concentration
CL/F	Apparent oral clearance

NOTES:

- Additional parameters may be included as required.

All the derived parameters described above will be listed. For each of these parameters, except t_{max} and t_{lag} , the following summary statistics will be calculated for each treatment group: n, arithmetic mean, standard deviation (SD), median, minimum, maximum, geometric mean with associated 95% CI, standard deviation of logarithmically transformed data, and the between-participant CV (%CVb) (where $\%CVb = 100 * \sqrt{(\exp(SD^2) - 1)}$ based on the geometric mean for the log-transformed PK parameters. For t_{max} and t_{lag} , median, maximum, minimum, arithmetic mean and standard deviation will be calculated.

